4.3 Follow-up procedures

There will not be any follow up procedures in this study. The non-contrast CT and the CG-SDCT will be the only portion of patient interaction.

5 STUDY EVALUATIONS AND MEASUREMENTS

The non-contrast chest CT or TAVR CT and CG-SDCT will be obtained from all eligible enrolled subjects for inclusion in the reader study. Clinical calcium scoring will be performed using conventional software by trained personnel. Calcific lesions in the distribution of the coronary arteries will be identified on tomosynthesis images and a total score also derived. Readers will be blinded to the calcium score from the other modality. Reader confidence in image quality will also be assessed on a 1 to 10 scale.

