3 INVESTIGATIONAL PLAN

3.1 Study Design

This is a one arm study of 20 patients who have undergone a clinical, outpatient non-contrast CT at UNC Hospitals for any pathological condition of the chest who consent to undergo an experimental s-DCT.

The study scan, s-DCT, will be performed within four weeks of his/her clinical evaluations by chest CT or a TAVR CT. There cannot be any intervening therapies or procedures (i.e. line placement, biopsy or excision of lesions) done in between the CT chest imaging and the s-DCT.

For patients that receive a CT for transcatheter aortic valve replacement (TAVR), this will require an expansion of the field of view from 5cm to 15cm coverage. This group of patients will receive an additional dose of approximately 30 mSv and these patients must be consented to participate prior to receiving their clinical CT.

Images will be acquired by a trained radiology technologist. The scan will consist of the following procedure. First, the patients, will be asked to change into a hospital gown. The technologist will comfortably position the patient in the supine position on the imaging table. EKG leads will be placed in appropriate positions to derive an EKG signal. Once the EKG signal is verified, the R wave will be selected for triggering the x-ray source. The subject will be asked to hold their breath, then the gated scan will be performed in an anterior-posterior direction. We anticipate that a breath hold of approximately 25 to 30 seconds will be required for the subject, with a single image acquired during each R wave. Images will be reconstructed off-line and transferred for review on conventional PACS workstations. Total patient preparation and imaging time should not exceed 20 minutes.

A reader study will be performed after all patients have been accrued. Each of the scans will be de-identified. As reading of all tests will take place after the patient has undergone clinical decision-making (treatment versus following), the results of this study will not affect patient care. Clinical calcium scoring will be performed using conventional software by trained personnel. Calcific lesions in the distribution of the coronary arteries will be identified on tomosynthesis images and a total score also derived. Readers will be blinded to the calcium score from the other modality. Reader confidence in image quality will also be assessed on a 1 to 10 scale.

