6 STATISTICAL CONSIDERATION

6.1 Primary Endpoint

The primary endpoint for this study is the CACS measured from chest tomosynthesis as compared to conventional CT (reference standard).

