6.3 Statistical Methods

We will be collaborating with a biostatistician for this research project. We will perform linear regression and Bland-Altman analysis to examine the relationship between the CT derived CACS and tomosynthesis scores. We anticipate that with at least 20 subjects, we will be able to evaluate a correlation coefficient between the two techniques of at least 0.6 or better with alpha of 0.05 and power of 0.83. With 20 patients at a correlation coefficient of .6 we expect 95% Confidence Intervals (CI) to be between .215 and .823. Using Bland-Altman analysis we hope to find a difference in the mean that is within a margin of 25%. We will calculate sens/spec. This will be exploratory; we do not believe that this method will reveal lesions not shown by the gold standard.

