8 DATA COLLECTION AND MANAGMENT

The non-contrast chest CT or TAVR CT and s-DCT that are obtained of all eligible enrolled subjects will be de-identified for inclusion in the readers study. Framingham risk scores will be obtained from clinical records. Copies of the clinical report forms as well as the de-identified images described in the preceding will be submitted for each case to the Study Coordinators for maintaining the study record and entering the data into a spreadsheet in preparation for the CACS study.

The source documents used during the reader study will be stored by the research coordinator for source verification. These data will be entered into an Excel spreadsheet by a research assistant or research coordinator. No identifying data

will be entered into the spreadsheet. This spreadsheet will be stored on the shared network storage for the Department of Radiology. Only the study team will have access to the spreadsheet.

Patient imaging data will be coded with a study ID number. No identifying patient information (besides consent forms) will be used in the study. All PHI will only be stored in Epic. A linkage file with the study ID and Medical Records # will be maintained in order to minimize risk and maintain confidentiality. Patient images will be de-identified prior to the reader study portion of this study.

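### Readers are blinded to the other modality's score but not to its images, and nothing else in the plan keeps the two reads independent

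*Combined protocol and SAP*

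**What the plan says.** The blinding rule appears in the same words in section 3.1 (Study Design) and section 5 (Study Evaluations and Measurements): "Readers will be blinded to the calcium score from the other modality".

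The text around it describes two scoring tasks. For CT, "Clinical calcium scoring will be performed using conventional software by trained personnel". For tomosynthesis, calcific lesions along the coronary arteries are identified and a total is derived; no software or scoring algorithm is named.

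On timing and coding, section 3.1 says "A reader study will be performed after all patients have been accrued" and "Each of the scans will be de-identified". Section 8 adds "Patient imaging data will be coded with a study ID number" and "A linkage file with the study ID and Medical Records # will be maintained", and repeats that images are de-identified before the reader study.

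Section 6.1 makes the comparison of tomosynthesis CACS with CT the primary endpoint, with CT as reference standard. Section 6.3 gives the analysis: "We will perform linear regression and Bland-Altman analysis to examine the relationship between the CT derived CACS and tomosynthesis scores". It adds sensitivity and specificity as exploratory.

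**The concern.** A method comparison needs the index test to be read without knowledge of the reference test. Withholding the reference number secures only part of that. The CT images show where calcium lies, and a reader who has seen them can look in those places on tomosynthesis without ever being told a score. The stated rule would be obeyed and the reads would still not be independent.

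Tomosynthesis scoring looks like the more exposed step, because as described it rests on a reader identifying lesions, whereas CT scoring uses conventional software.

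The primary comparison is at stake. Shared information between the reads pushes every agreement measure the same way, towards better agreement, and no later analysis can remove it. Section 1.2 says that success could promote larger studies or even support tomosynthesis as the standard modality for calcium scoring, so optimistic agreement would carry forward.

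**Working it through.** **Planning figures.** The point disputes none of them; they are reproduced first to show this. All use a test of zero correlation with two-sided alpha 0.05 (sidedness is not stated in the plan) and r = 0.6.

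- 95% CI at n = 20, Fisher z: tanh(atanh(0.6) ± 1.96/√17) = tanh(0.693 ± 0.475) = 0.214 to 0.824. Sections 6.3 and 6.4 state .215 to .823, which agrees to rounding.
- Power at n = 20, Fisher z with bias correction: Φ(√17 × (0.693 + 0.6/(2 × 19)) − 1.96) = Φ(0.963) = 0.832. Simulation of the bivariate-normal t-test gives 0.836. Section 6.3 states 0.83.
- Minimum n: the noncentral-t (fixed-x) model gives power 0.797 at n = 16 and 0.824 at n = 17. Section 6.4 states 17.

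The sample size needs no change for this point.

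**What the safeguards close.** No arithmetic applies to the blinding itself, so each provision is set against the route it would have to close.

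| Provision | Closes | Leaves open |
|---|---|---|
| Blinding to the other modality's score (3.1, 5) | Being told the score; also scoring CT and then knowingly reading the same patient's tomosynthesis | Seeing the other modality's images |
| De-identification of each scan (3.1, 8) | Recognition by name | Matching by label, if both scans carry the same one, or by distinctive appearance among 20 patients |
| Study ID with a linkage file to the medical record number (8) | Identifiers in the study data | Whether readers see the ID, and whether CT and tomosynthesis carry the same one. Linkage to a medical record number suggests one ID per patient, but the text does not say |
| Reader study after full accrual (3.1) | Any effect of the reads on care | Order, spacing and sessions. Both sets are available by then and no separation is specified |
| CT scored by trained personnel (3.1, 5) | Nothing by itself | Whether those people also read tomosynthesis |

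Section 7.3 also has every study reviewed within 7 days for concerning lesions. It does not say whether that reviewer may later be a reader.

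**Direction of effect.** If a reader looks on tomosynthesis where CT showed calcium and discounts sites where it did not, the tomosynthesis total moves towards the CT total. Correlation rises, the Bland-Altman mean difference and spread shrink, and sensitivity and specificity rise. The direction follows from the mechanism; the amount depends on reading conduct that the plan does not describe.

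**The case against.** The strongest reply is that the rule, followed in spirit, already excludes the worst case. Someone who has just scored a patient's CT and can recognise that patient is not blinded to the CT score when reading the tomosynthesis. CT scoring and tomosynthesis reading are described as separate tasks and may be done by different people. Reading labels may differ by scan; the text does not exclude it. Session plans and code lists are often kept in a reader manual. This is also a 20-patient first-in-human study whose images do not affect care.

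Much of this stands. It makes the bias conditional and narrows the gap to the other modality's images and to how blinding is maintained. It does not close that gap: the written rule is specific, it names the score alone, and nothing elsewhere in the protocol extends it.

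Three stronger readings are tempting and are not supported.

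- *That readers will see a shared ID, or read both scans in one sitting.* The documents state neither. They only fail to rule them out.
- *That modest recall would carry a poor modality to the target.* Suppose the recorded tomosynthesis score is (1 − w) times an independent read plus w times the CT score, with equal SDs. The observed correlation is then ((1 − w)r + w)/√((1 − w)² + w² + 2w(1 − w)r), so a true r of 0.40 appears as 0.49, 0.58 and 0.67 at w = 0.1, 0.2 and 0.3. The arithmetic is right, but w has no source in the documents. The model also describes recall of the CT score, which the rule withholds, not guidance from CT images.
- *That 0.6 is a pass mark.* In sections 6.3 and 6.4 it is the value used for power, sample size and the expected interval. No decision turns on observing it.

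**Conclusion.** The concern holds as a cheap improvement. The plan blinds readers to the other modality's score only and has no separate reading codes, order, sessions or reader assignment to keep the two reads independent. If one person reads both modalities, or a tomosynthesis reader sees the CT images, agreement would be biased upward in the primary comparison and in the exploratory sensitivity and specificity.

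This rests on two conditions the documents leave open: that CT images reach the tomosynthesis reader, and that a patient's two scans can be matched. No size can be given. Partial dependence would bias the estimates without making them meaningless. The planning figures in sections 6.3 and 6.4 are unaffected.

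**What to change.** Amend sections 3.1 and 5 before any reading starts, so that they state:

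1. Readers are blinded to both the images and the calcium score of the other modality.
2. Each modality has its own random reading code, and the key is not available to readers.
3. The full tomosynthesis set is read first, in random order, and its scores are locked.
4. CT is then scored in a separate later session, or by the CT-scoring personnel without access to the tomosynthesis images or scores.

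The cost is a second code list, a reading schedule and a somewhat longer reading period. No extra readers, scans or patients are needed.

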6 STATISTICAL CONSIDERATION

6.1 Primary Endpoint

The primary endpoint for this study is the CACS measured from chest tomosynthesis as compared to conventional CT (reference standard).

6.3 Statistical Methods

We will be collaborating with a biostatistician for this research project. We will perform linear regression and Bland-Altman analysis to examine the relationship between the CT derived CACS and tomosynthesis scores. We anticipate that with at least 20 subjects, we will be able to evaluate a correlation coefficient between the two techniques of at least 0.6 or better with alpha of 0.05 and power of 0.83. With 20 patients at a correlation coefficient of .6 we expect 95% Confidence Intervals (CI) to be between .215 and .823. Using Bland-Altman analysis we hope to find a difference in the mean that is within a margin of 25%. We will calculate sens/spec. This will be exploratory; we do not believe that this method will reveal lesions not shown by the gold standard.

6.4 Sample Size and Power

With a power of .8 and alpha of .05 we need 17 patient sample size to detect an absolute correlation of 0.6. Since we are recruiting at least 20 subjects, we are meeting our minimum sample size. With a sample size of 20 patients at an R of .6 our 95% confidence intervals will be between .215 and .823. These confidence intervals do not cross zero.

6.5 Secondary Analysis

The 30 ms cardiac EKG trace will be extracted for each of the projections. Then, a Pearson correlation coefficient will be calculated for each of the projections relative to the first x-ray projection. The mean of the Pearson of the correlation coefficients will then calculated and served as an estimate of the timing precision of each projection set for each patient. The mean and standard deviation of the correlation coefficients will be reported.

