2.2 Secondary Objectives

The secondary objectives of this study are:

- To evaluate the practicality of using CG-SDCT in terms of image quality and artifacts.
- To determine the accuracy of gating, which is measured by the correlation of the between the x-ray pulses and the EKG R-wave within a 30ms window around the x-ray pulse.

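### Section 6.5 measures how consistent the EKG traces are with the patient's first beat, so it does not answer the Section 2.2 objective of gating accuracy against the R-wave.

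*Combined protocol and SAP*

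**What the plan says.** Section 2.2 states the objective: "To determine the accuracy of gating, which is measured by the correlation of the between the x-ray pulses and the EKG R-wave". The window is placed by the pulse: "the EKG R-wave within a 30ms window around the x-ray pulse".

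Section 6.5 is the only analysis of gating. Its data step is "The 30 ms cardiac EKG trace will be extracted for each of the projections". Its comparison is that "a Pearson correlation coefficient will be calculated for each of the projections relative to the first x-ray projection". The coefficients are averaged, and the average is "served as an estimate of the timing precision of each projection set for each patient". The output is limited to this: "The mean and standard deviation of the correlation coefficients will be reported".

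Section 3.1 describes the acquisition: "Once the EKG signal is verified, the R wave will be selected for triggering the x-ray source". It expects "a breath hold of approximately 25 to 30 seconds will be required for the subject, with a single image acquired during each R wave". No section describes a check of where the pulses fell relative to the R peak, and none gives a tolerance for gating.

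**The concern.** The objective names an external reference, the R-wave. The analysis replaces it with an internal one, the same patient's first trace. The wording changes with it, from accuracy to precision. A measure of agreement among pulses can show that they fall at the same point of the cycle. It cannot show that this point is the R-wave.

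Two things are at stake. First, a reader could take a high mean r as evidence of accurate gating, which it is not. Second, all of a patient's coefficients share one reference beat, so ordinary timing variation in that beat moves the whole patient mean. Part of the SD reported across patients would then be chance in single beats. Aim 1 is the first human use of the gated system, and gating accuracy is one of only two secondary objectives.

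**Working it through.** The plan gives no figure to reproduce here: there is no threshold, tolerance or precision target for gating.

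**1. Side by side.**

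| | Section 2.2 | Section 6.5 |
|---|---|---|
| Quantity named | accuracy | timing precision |
| Reference | EKG R-wave | the patient's first projection |
| Data | 30 ms window at the pulse | 30 ms trace per projection |
| Output | a correlation with the R-wave | mean and SD of r |

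**2. Shared offset, no noise or jitter.** Let E(t) be the EKG and d an offset common to all pulses. Every trace is x_k(t) = E(t + d). All traces are then identical and corr(x_1, x_k) = 1 whatever d is. Numerically, r = 1.0000 at each of eleven offsets from -200 to +300 ms. This result does not depend on the waveform.

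**3. With jitter and noise.** Let e_k be the jitter of pulse k, x the EKG in the window at offset d, x' its slope, ρ the correlation of x with x' over the window, and σ² the noise variance. For small jitter,

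1 − r ≈ ½ (e_k − e_1)² × [Var(x′)/Var(x)] × (1 − ρ²),

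and noise multiplies r by about Var(x)/(Var(x) + σ²). The offset acts only through the shape of the EKG in the window. Nothing in the formula returns d or its sign. On flat EKG, Var(x) is near zero and r goes to about 0.

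**4. Illustration.** The documents give no waveform, noise, jitter, sampling rate or number of projections, so all are assumed: a sum-of-Gaussians EKG with R-wave SD 8 to 12 ms, noise 1 to 2% of R amplitude, 1 kHz sampling and a window centred on the pulse. One image per R wave over 25 to 30 s gives 25 × 60/60 = 25 to 30 × 80/60 = 40 projections at an assumed 60 to 80 bpm. Mean r against the first projection:

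| Jitter SD | Centred | 20 ms late |
|---|---|---|
| 0.5 ms | 0.97–0.99 | 0.99–1.00 |
| 1 ms | 0.93–0.96 | 0.99–1.00 |
| 3 ms | 0.69–0.74 | 0.91–0.99 |

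- Direction: 20 ms early gives 0.94–0.99 at 3 ms jitter, overlapping 20 ms late.
- Larger shifts (0.5 ms jitter): 0.79–1.00 at 30 ms late, 0.00–0.99 at 50 ms, about 0 at 80 ms.
- Narrower R wave (SD 5–7 ms, 1–2% noise, 3 ms jitter): 0.56–0.97 at 20 ms late, so r may be below or above the centred value of 0.65–0.72.
- Narrower R wave and 5% noise (0.5 ms jitter): 0.88–0.96 late against 0.96–0.98 centred, so r falls.
- Window placement (3 ms jitter): an on-time pulse at either end of the window gives 0.947–0.985, against 0.696–0.724 when centred.

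**5. One reference beat.** By step 3, the patient mean of 1 − r is proportional to an average of squared jitter differences. With normal jitter of variance τ² and N projections, that average has variance 2τ⁴[1 + 3/(N − 1)] against the first beat and 8τ⁴/(N − 1) over all pairs. The ratio of SDs is √[(N + 2)/4]. At N = 29 this is √7.75 = 2.78. Simulation with identically gated patients agrees: the SD of the patient mean is 0.032 to 0.035 against 0.012 at 1 ms jitter (ratio 2.7 to 2.9), and about 0.15 against 0.05 at 3 ms.

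**6. Check of the alternative.** In simulation, pulse time minus detected R-peak time recovered true offsets of -20 to +20 ms within 0.3 ms, and jitter SDs of 0.5, 1 and 3 ms as 0.49–0.56, 0.94–1.06 and 2.83–3.10. For a centred window and 3 ms jitter, the share of R peaks inside ±15 ms is Φ((15 − 10)/3) = 95.2% at a 10 ms offset and Φ((15 − 20)/3) = 4.8% at 20 ms; simulation gave 94–96% and 4–6%.

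**The case against.** The strongest defence is that Section 6.5 is simply the working form of a loosely worded objective, and that it labels its result precision and does not claim accuracy. The R wave triggers the source and the EKG signal is verified first, so the first trace is a reasonable stand-in for the R-wave. The measure is descriptive, in 20 patients, and nothing depends on it.

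Much of this stands as a limit on the consequence. It does not close the gap: triggering on the R wave is the function that Section 2.2 sets out to test, and nothing checks where the first pulse fell.

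The simulation is also open to attack, because its inputs are assumed and the pattern changes with them. That stands too. A reader might infer from the table in step 4 that mistimed sets always score at least 0.9, or always above well-timed ones. The documents fix neither the R width, the noise nor the position of the pulse in the window, and the results for narrower R waves and more noise show that r can fall. A reader might also infer that r is blind to any offset; large shifts can drive it to about 0. The supported statement is that r cannot be read as accuracy in either direction.

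Using a single reference trace is a common and simple choice. The objection that all pairs is only an efficiency gain is fair, but the gain is nearly threefold in SD and needs no new data.

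**Conclusion.** The point holds. The stated objective is accuracy against the R-wave, and the only analysis delivers consistency with the patient's first beat. This rests on the text and on the algebra of step 2, without any simulated figure. The size of the effect of a real offset on r is illustrative only. The factor of about 2.8 for the single reference beat rests on small normal jitter and an assumed 29 projections.

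A reader might infer that the gating is in fact offset, or that first beats are mistimed. The documents give no timing data and do not support either. Nor is the primary calcium-score comparison affected: the correlation enters no decision and has no threshold. The change is worth making because, without it, one of two secondary objectives is only partly answered.

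**What to change.** Replace the analysis in Section 6.5 with:

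> Pulse time minus R-peak time (ms) will be computed for each projection. Per patient, the mean (accuracy), the SD (precision) and the percentage of projections with the R peak inside the 30 ms window around the pulse will be reported, then summarised over patients.

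State where the pulse sits in the window, since both the percentage and any correlation depend on it.

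If a correlation is kept, average it over all pairs of projections and report it only as trace consistency. Do not substitute a correlation with an R-peak-centred template as the accuracy measure. In simulation it was only about -0.1 to 0.3 at 10 ms late, where about 95% of R peaks are still in the window. It also does not fall steadily with offset (-0.86 to -0.43 at 30 ms, -0.17 to 0.41 at 50 ms).

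If the continuous EKG or synchronised pulse times are not retained, which the documents do not say, use the all-pairs average and restate both objective 2.2 and the result as trace consistency across projections.

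Cost: revised wording, a peak-detection step, and reliance on stored EKG and pulse timestamps. No extra scans are needed. The fallback gives up the accuracy objective.

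### Section 6.5 scores each patient's timing precision against the first projection only, so the score depends on pulse order: a mistimed first pulse costs N-1 times as much as the same error later.

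*Combined protocol and SAP*

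**What the plan says.** Section 2.2 lists gating accuracy as a secondary objective, measured by the "correlation of the between the x-ray pulses and the EKG R-wave within a 30ms window around the x-ray pulse". Section 6.5 gives the only planned analysis of it:

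- **Data:** "The 30 ms cardiac EKG trace will be extracted for each of the projections".
- **Reference:** "a Pearson correlation coefficient will be calculated for each of the projections relative to the first x-ray projection".
- **Score:** the mean of these correlations, which "served as an estimate of the timing precision of each projection set for each patient".
- **Report:** "The mean and standard deviation of the correlation coefficients will be reported". The text does not say whether this SD is within or between patients.

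Section 3.1 describes the acquisition: one image per heartbeat ("with a single image acquired during each R wave"), and "a breath hold of approximately 25 to 30 seconds will be required for the subject". Before the scan, "Once the EKG signal is verified, the R wave will be selected for triggering the x-ray source". No section checks that the first pulse is well timed, gives a rule for replacing a bad reference, or names another reference trace for the analysis. The number of projections per scan is not stated.

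**The concern.** A measure of how consistently a set of pulses was timed should not change when the same pulses are put in a different order. This one does. Every correlation in a patient's score shares the first trace, so any timing error in that trace enters all of them, while an error in a later trace enters only one.

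The study aims at the first cardiac-gated use of this system in humans, with about 20 patients and one gating value each. A single poor first trigger could give an otherwise well-gated patient a very low value. Ordinary jitter in the first pulse also adds spread between patients that has nothing to do with how well they were gated.

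**Working it through.** The plan gives no target or figure for this analysis, so there is none to reproduce.

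**Number of projections (assumption).** With one image per beat over 25 to 30 s, and an assumed heart rate of 50 to 100 per minute, N lies between 25 × 50/60 ≈ 21 and 30 × 100/60 = 50. I use about 20 to 50, with N = 29 for illustration.

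**One mistimed pulse.** Let a be the correlation between two well-timed traces and b that between a mistimed and a well-timed trace. The score is the mean of the N-1 correlations with projection 1.

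- First pulse mistimed: score = b, a loss of (a-b).
- One later pulse mistimed: score = ((N-2)a + b)/(N-1), a loss of (a-b)/(N-1).
- Ratio of losses: N-1, for any EKG shape; about 19 to 49 for N of 20 to 50.

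With a = 0.98, b = 0 and N = 29, the score is 0.00 if the first pulse is off and (27 × 0.98)/28 = 0.945 if a later one is. Read literally, section 6.5 also counts the first projection against itself (r = 1). The scores are then 0.034 and 0.947, and the ratio is still N-1.

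**All-pairs mean.** One mistimed pulse lowers it by 2(a-b)/N wherever it falls: 0.98 - 2 × 0.98/29 = 0.912.

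**Simulation (all inputs assumed).** Synthetic QRS with an R wave of SD 10 ms, 30 ms window centred on the peak, 1 ms sampling, jitter SD 1.5 ms, 2% noise, N = 29, one pulse shifted, 300 replicates. Self-correlations are excluded.

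| Shift | Planned score, first pulse off | Planned score, later pulse off | All pairs, either | Leave-one-out average, either |
|---|---|---|---|---|
| none | 0.905 | 0.905 | 0.903 | 0.949 |
| 5 ms | 0.591 | 0.893 | 0.88 | 0.94 |
| 10 ms | 0.192 | 0.878 | 0.853 | 0.920 |
| 15 ms | -0.081 | 0.865 | 0.834 | 0.910 |
| 20 ms | -0.291 | 0.855 | 0.820 | 0.903 |

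**No mistimed pulse, the same 2 ms jitter in every patient.** Two separate runs, window at the peak, self-correlations excluded:

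- Between-patient SD 0.094 planned against 0.032 all pairs (ratio 2.9), and 0.083 against 0.032 (ratio 2.6).
- Cohort mean 0.842 planned against 0.846 all pairs, and 0.853 against 0.845. There is no bias here, as expected when the pulses are exchangeable.
- The planned SD falls to 0.027 with 1 ms jitter, and to 0.021 with 2 ms jitter and the window 10 ms before the peak. Over the settings tried it ranged from about 0.005 to 0.09.

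**Would a within-patient SD reveal the problem?** With a = 0.98, b = 0 and N = 29, a later error gives an SD of 0.98/√28 = 0.19. A first-pulse error makes all 28 correlations equal to b, so the SD is 0. In simulation with the window 10 ms early and a 15 ms error, the within-patient SD was about 0.31 when the 11th pulse was off but only 0.05 when the first was.

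**The case against.** The strongest reply is that section 6.5 is a descriptive secondary analysis with no test, threshold or pass mark, and that the primary calcium-score comparison does not use it. That stands, and it limits the severity. It also stands that N, EKG shape, jitter, noise, sampling rate and window position are all assumed. Only the N-1 ratio is free of the waveform assumptions.

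A reader might infer several stronger claims that the documents do not support:

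- **That the planned rule doubles the shortfall from perfect correlation.** A simulated shortfall of 0.149 against 0.083 arises only when trace-to-trace correlations are compared with trace-to-average ones. That is a change of scale. Against all pairs the means agree.
- **That spurious spread is five times too large, so results mainly reflect each patient's first beat.** The ratio of five (0.090 against 0.018) also uses the average-trace scale. Against all pairs it is about 2.5 to 3, and the absolute spread is small at lower jitter or another window position.
- **That a later error goes unseen.** It has little effect on the mean. If the reported SD is within-patient, it would show there.
- **That a patient would be classed as a gating failure.** The plan defines no such category.
- **That a mistimed reference is likely somewhere in the cohort.** The chance that at least one of 20 first pulses is mistimed is 1-(1-p)^20: 33% at p = 2%, 64% at p = 5%, but about 10% at p = 0.5%. The documents give no p, so these figures rest wholly on the assumed rate.

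One could also say that the larger gap is elsewhere. Section 2.2 defines accuracy against the R-wave, and a within-patient reference cannot detect a delay common to all pulses: a simulated common 20 ms shift still scored 0.995, against -0.30 with an R-wave template. That is true, but it is a separate point. The planned score is order-dependent even as a measure of consistency.

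**Conclusion.** The concern holds as a minor-to-moderate point. The per-patient score in section 6.5 depends on pulse order, and nothing elsewhere in the protocol corrects this. A mistimed first pulse lowers the score N-1 times as much as the same error on one later pulse, about 19 to 49 times for an assumed N of 20 to 50. With no mistimed pulses, the between-patient SD is inflated about 2.5 to 3 times relative to all pairs under the assumed waveform and jitter, while the cohort mean is unaffected. The reported SD is not a safeguard: it is not said to be within-patient, and a within-patient SD would not reliably flag a bad first pulse.

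**What to change.** In section 6.5, replace the first projection as reference with the mean of all distinct pairwise correlations within the patient, leaving out self-correlations. Report the per-patient mean together with both the within-patient and the between-patient SD, and say which is which.

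The average trace of the patient's other projections is an acceptable alternative reference. It gives higher values (0.949 against 0.903 in the error-free simulation), so one of the two must be named in advance. Under either, a single mistimed pulse moves the mean only modestly, which is why the within-patient SD should be reported beside it.

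The cost is a short change of wording and a few lines of code on traces that will be extracted anyway, with no new data, readers or patients. The values will not be comparable with any earlier results computed against the first projection, so that version can be kept as a sensitivity line. The change does not supply the accuracy against the R-wave named in section 2.2, which needs its own reference.
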